3.3.8. HIV Status

Baseline HIV status will be based on subject report at the enrollment visit. Subjects who have not been previously diagnosed with HIV and who have not recently tested negative for HIV will be offered HIV testing per the standard clinical practice at each site. For subjects who are tested at baseline, their baseline HIV status will be based on the results of the testing.

At each follow-up visit, any changes to the subject's HIV status will be documented.

3.3.9. Antacid Use Status

Antacid use will be assessed at baseline, Visit 2, and Visit 3. Subjects who report use of antacids at baseline or follow-up visits as documented on the Visit Documentation form will be classified as using antacids. Subjects who do not report antacid use at all study visits will be classified as not using antacids.

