6.5 Concomitant Medications/Treatments

Administration of any medications will be recorded on the appropriate DCF. Concomitant medications will include all medications taken 21 days before initiating study treatment through

Visit 3 or early termination, whichever occurs first. Prescription and over-the-counter (OTC) medications (including antacids) will be included, as well as, herbs, vitamins, and other supplements. Previously recorded medications will be updated as appropriate.

Subjects who have received study drug and are subsequently diagnosed with a concomitant infection that requires systemic antibiotics will receive treatment according to the local clinic's standard clinical practice, which will avoid antibiotics active against CT if a suitable alternative is available. Subjects who receive antibiotics active against CT after study drug administration will remain in the trial and followed for safety and efficacy. The medications that are prohibited for study eligibility in Section 5.2 are also prohibited throughout study participation.

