4.4.7. Prior and Concomitant Therapy

Administration of any medications will be recorded on the appropriate DCF. Concomitant medications include all medications taken 21 days before initiating study treatment through Visit 3 or early termination, whichever occurs first. Prescription and over-the-counter (OTC) medications (including antacids) is included, as well as, herbs, vitamins, and other supplements. Previously recorded medications are updated as appropriate.

Subjects who have received study drug and are subsequently diagnosed with a concomitant infection that requires systemic antibiotics receive treatment according to the local clinic's standard clinical practice, which avoids antibiotics active against CT if a suitable alternative is available. Subjects who receive antibiotics active against CT after study drug administration remain in the trial and followed for safety and efficacy. The medications that are prohibited for study eligibility in protocol Section 5.2 are also prohibited throughout study participation.

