9.1.1. Prior and Concomitant Medications

The use of prior and concomitant medications taken during the study will be recorded on the Concomitant Medication CRF. Concomitant medications will be coded to the Anatomical Therapeutic Classification using the WHO Drug Dictionary. Individual subject listings will be generated for all concomitant medications ([Listing 10](#)). A summary of antiretroviral therapy among HIV positive subjects and PrEP use among HIV negative subjects at baseline and follow-up will be presented ([Table 43](#)).

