		“Previous” Partners	x/NA	Yes/No/NA (Always/Sometimes/Never)	Yes/No (Always/Sometimes/Never)		xxxx, xxxx, xxxx,	xxxx, xxxx, xxxx,	xxxx, xxxx, xxxx,	

^a The timeframe for the number of Sexual Partners is “in the past 60 days” (prior to enrollment). The timeframe at the screening visit for the Number of New Partners is “in the past week”, while the timeframe for the Number of Previous Partners is “in the past 60 days”. The timeframe for the Number of New and Previous Partners at the follow-up visits is “since the last visit”.

Implementation Notes:

1. Sort order will be by Actual Treatment Group, Subject ID.
2. If all subjects received the correct treatment, only display “Treatment Group”.
3. If the subject reported no anal receptive sex, then the corresponding anal receptive sex cells will all be “NA”.
4. Missing responses will be populated with “Not Reported”.

Listing 10: Concomitant Medications - All Enrolled Subjects

Actual Treatment Group	Randomized Treatment Group	Subject ID	Concomitant Medication Number	Medication	Medication Start Day	Medication End Day	Indication	ATC 1 / ATC 2	Taken for a SAE? (AE Description; AE Number)	Taken for HIV or an STD?
Azithromycin/Doxycycline	Azithromycin/Doxycycline	xxxxxx	xx	xxxxxx	xx	xx	xxxxxx	xxxx / xxxx	Yes/No xxxxx; xx	Yes/No
Azithromycin/Doxycycline	Azithromycin/Doxycycline	xxxxxx	xx	xxxxxx	xx	xx	xxxxxx	xxxx / xxxx	Yes/No xxxxx; xx	Yes/No

Implementation Notes:

1. Sort order will be by Actual Treatment Group, Subject ID, Concomitant Medication Number.
2. 'Medication Start Day' and 'Medication End Day' are relative to enrollment (which is Day 1, day before enrollment is Day -1). For medication start dates that are > 30 days prior to enrollment, rather than use exact days, categorize as follows:
 - > 5 years prior to enrollment
 - 1- 5 years prior to enrollment
 - 1-12 months (exclusive of 12 months) prior to enrollment.
 - For 'Medication End Day', if medication is ongoing, display 'Ongoing' in the Medication End Day' column.
 - For 'Medication End Day', if end of medication is unknown, display 'Unknown' in the 'Medication End Day' column.
3. If a Medication is taken for a SAE, then concatenate the conmed with the Adverse Events by AENUM and report the AETERM.
4. If all subjects received the correct treatment, only display a single "Treatment Group" column.

Listing 11: Treatment Adherence Data

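### Antacid use is classified from a report at any visit, with no link to the dosing days, so men who took antacids only after the course count as users in Tables 31-33

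*SAP*

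**What the plan says.** The exploratory objective (Protocol 3.1.3, SAP 3.1.3) includes the effect of antacid use on Day 29 cure. SAP 3.3.9 defines the variable in three sentences. The first sets the times: "Antacid use will be assessed at baseline, Visit 2, and Visit 3". The second defines users: "Subjects who report use of antacids at baseline or follow-up visits as documented on the Visit Documentation form will be classified as using antacids". The third defines the rest: "Subjects who do not report antacid use at all study visits will be classified as not using antacids".

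SAP 6.4 and 8.2.3 carry the variable into the subgroup summaries without adding a time limit. Tables 31-33 use it in the CC, ITT and PP populations. (The implementation note under the shells numbers the antacid tables 32-34, but their titles run 31-33.) They follow the Table 19 layout: cure by arm, and doxycycline minus azithromycin, within each stratum.

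Medications are also recorded separately. Protocol 6.5 covers antacids by name: "Prescription and over-the-counter (OTC) medications (including antacids) will be included". SAP 9.1.1 says where: "The use of prior and concomitant medications taken during the study will be recorded on the Concomitant Medication CRF". Listing 10 gives a start and an end day for each medication. Listing 11 gives the days taken to finish the doxycycline (or placebo) capsules.

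**The concern.** The objective makes sense only if the exposure is antacid use while study drug was being taken. That premise is not written in either document, but it is the natural reason to ask the question. The rule in SAP 3.3.9 does not measure that exposure. It counts a report at any of three visits, and only the Visit 2 report is sure to cover the course; that report also takes in about a week after it.

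The other subgroup variables are anchored in time. LGV, HIV and symptomatic status are taken at baseline (SAP 3.3.7, 3.3.8, 3.3.10), and adherence is counted in days from the completed initial dose (SAP 3.3.4, 3.3.5). Antacid use alone combines reports from before, during and after treatment. At stake is whether Tables 31-33 can be read at all: similar results in the two strata could mean that antacids make little difference, or that the user stratum holds many men who took none during dosing.

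**Working it through.** Neither document gives an antacid rate, effect size or power, so there is no plan figure to reproduce. The check sets the time windows side by side and then works out the expected direction.

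**Step 1: windows**

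| Item | Days | Source |
|---|---|---|
| Azithromycin or placebo capsules | Day 1 | Protocol 6.2 |
| Doxycycline or placebo, planned | 7 days from Day 1 | Protocol 6.2 |
| Adherence window | 10 days from the completed initial dose | SAP 3.3.4 |
| Visit 2 | Day 15 (12-18) | Protocol 7.3 |
| Visit 3 | Day 29 (25-31) | Protocol 7.4 |
| Medication recall at Visit 3 | since the previous visit | Protocol 7.4 |

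Recall at Visit 3 thus covers about Day 15 to Day 29. Even with Visit 2 at its earliest, Day 12, it starts after Day 10. There are two exceptions. If Visit 2 was missed, recall reaches back into the course. Retreatment within 48 hours can move the adherence window by up to two days, to about Day 12. This recall period is that of the medication interview; the period for the Visit Documentation form is not given, and I assume it is the same.

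**Step 2: how the rule treats typical cases**

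| Antacid taken | Reported at | Class under SAP 3.3.9 | Overlaps dosing? |
|---|---|---|---|
| Days 2-5 | Visit 2 | User | Yes |
| Day 11 only, capsules finished on Day 7 | Visit 2 | User | No |
| Day 20 only | Visit 3 | User | No |
| Before the first dose | Baseline only | User | Not known; look-back not stated |

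**Step 3: direction**

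Let *e* be the share of classified users who took an antacid during dosing. Assume accurate reporting, no true users among the non-users, the same *e* in both arms, and men who used antacids only outside dosing being cured at the same rate as non-users.

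- User stratum, cure in one arm: *e* × (cure if exposed) + (1 − *e*) × (cure if unexposed). The user-minus-non-user gap in that arm is therefore *e* × the true gap.
- Treatment difference in the user stratum: *e* × D1 + (1 − *e*) × D0, where D1 and D0 are the true differences in exposed and unexposed men. The non-user stratum shows D0, so the two strata differ by *e* × (D1 − D0).

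Both contrasts shrink by the factor *e*:

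| Assumed true contrast | *e* = 1 | 0.75 | 0.50 | 0.25 |
|---|---|---|---|---|
| 20 points | 20 | 15 | 10 | 5 |
| 10 points | 10 | 7.5 | 5 | 2.5 |

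**Step 4: a range for *e***

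Take only the 29 days from Day 1 to Day 29, with no look-back before dosing. The course is 7/29 = 24% of that span. For sporadic use with daily chance *q* (an assumption), *e* = [1 − (1 − *q*)^7] / [1 − (1 − *q*)^29]. At *q* = 2% this is 0.132/0.443 = 0.30. At 1%, 5% and 10% it is 0.27, 0.39 and 0.55. For daily long-term users *e* = 1. If half of the classified users are daily users and half sporadic at 2%, *e* = 0.5 + 0.5 × 0.297 = 0.65.

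**The case against.** The strongest reply is that this is an exploratory summary. SAP 6.4 disclaims power for every subgroup, no interaction test or p-value is planned in Tables 31-33, and the primary and secondary results are untouched. That stands and limits the weight of the point. A reader might infer that the trial could wrongly conclude that antacids do not matter; the plan provides for no such conclusion.

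A reader might also infer an exposure window of about 50 days, by adding the 29 study days to the 21-day look-back in SAP 4.4.7: "Concomitant medications include all medications taken 21 days before initiating study treatment through Visit 3 or early termination, whichever occurs first". The documents do not support this. That rule governs the Concomitant Medication form, whereas SAP 3.3.9 classifies from the Visit Documentation form, whose look-back appears nowhere. The point does not need it, because a report at Visit 3 alone is enough.

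The tables report the difference between arms within each stratum, so the loss of a user-versus-non-user gap is not the loss of a planned estimate. That is correct. Step 3 shows that the planned treatment differences are drawn together in the same way, but the figures remain illustrations. If most users take antacids daily there is little or no dilution, and the documents do not say how antacids are used.

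Two further readings should be set aside. The third sentence of SAP 3.3.9 could be taken to put a one-visit reporter in both groups. It is loosely worded, but the second sentence already makes him a user, so the natural reading is no report at any visit. And recording exposure after the outcome may have been settled is not itself a fault: any use during Days 1-7 has to be collected at follow-up.

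Finally, the medication log is not a perfect source. As-needed use is dated imprecisely, and Listing 10 allows ongoing and unknown end days. The fix has to deal with that.

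**Conclusion.** The point holds as a definitional mismatch. As written, SAP 3.3.9 counts as exposed a man who took antacids only after his last capsule. The rule is stated, so this is more than a missing detail. The expected effect is to make the strata in Tables 31-33 look more alike, by the factor *e*. That direction rests on the Step 3 assumptions; it is expected, not certain, and could change if men who used antacids outside dosing differ from non-users in other ways that affect cure. The size cannot be computed from the documents: *e* could be near 1 if users take antacids daily, or about 0.27 to 0.55 under the assumed sporadic use. The consequence is confined to a named exploratory objective. It is worth correcting because the correction is cheap and the tables are hard to interpret without it.

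**What to change.** Revise SAP 3.3.9 before unblinding:

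- Define antacid use as an antacid record on the Concomitant Medication form whose start and end days overlap the period from Day 1 to the last study-drug dose, taken from the adherence data behind Listing 11. State which day stands in when the day of the last dose is not available.
- Count an ongoing or unknown end day as overlapping if the start day is on or before the last dose.
- Class men with no overlapping use as non-users, and reword the last sentence of the section to say so.
- Use this flag in Tables 31-33, and keep the any-visit flag as a sensitivity summary.

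The cost is SAP wording, one derived variable and the extra summaries. No new data are needed, since the plan already lists the medication days and the dosing data. The downsides are that as-needed use is dated imprecisely, that the rule for open-ended records will still count some men who took nothing during the course, and that the user stratum may be smaller. Making the change before unblinding keeps it from looking driven by the results.

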6.3.2. Efficacy Analyses

6.3.2.1. Intent-to-Treat Analysis (ITT) Population

The Intent-to-Treat (ITT) population includes all randomized subjects, regardless of whether they received study treatment, had a positive baseline rectal CT NAAT result, or were compliant with the administration procedures or schedule.

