6.5. Missing Data

Subjects with unknown microbiologic cure status will be excluded from the CC and PP population. For ITT analyses, such subjects will be included with their cure status imputed as microbiological failures.

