Table 28: Microbiologic Cure at Visit 3 (Day 29) by Treatment Group and Adherence to Treatment - CC Population

Table 29: Microbiologic Cure at Visit 3 (Day 29) by Treatment Group and Adherence to Treatment - ITT Population

Table 30: **Microbiologic Cure at Visit 3 (Day 29) by Treatment Group and Adherence to Treatment - PP Population**

Table 31: **Microbiologic Cure at Visit 3 (Day 29) by Treatment Group and Use of Antacids - CC Population**

Table 32: **Microbiologic Cure at Visit 3 (Day 29) by Treatment Group and Use of Antacids - ITT Population**

Table 33: **Microbiologic Cure at Visit 3 (Day 29) by Treatment Group and Use of Antacids - PP Population**

Table 34: **Microbiologic Cure at Visit 3 (Day 29) by Treatment Group and Baseline Symptomatic Status - CC Population**

Table 35: **Microbiologic Cure at Visit 3 (Day 29) by Treatment Group and Baseline Symptomatic Status - ITT Population**

Table 36: **Microbiologic Cure at Visit 3 (Day 29) by Treatment Group and Baseline Symptomatic Status - PP Population**

Implementation Notes:

For Tables 26 – 28, the subgroup labels will be “HIV Negative” and “HIV Positive”.

For Tables 29 – 31, four subgroups will be included in the summaries, two for the primary definition of adherence (with subgroup labels “Adherent – Primary Def’n” and “Not Adherent – Primary Def’n”) and two for the alternative definition of adherence (with subgroup labels “Adherent – Alternate Def’n” and “Not Adherent – Alternate Def’n”).

For Tables 32 – 34, the subgroup labels will be “No Antacid Use” and “Antacid Use”.

For Tables 35 – 37, the subgroup labels will be “Asymptomatic” and “Symptomatic”.

Table 37: Summary of Categorical Demographic and Baseline Characteristics by Site - All Enrolled Subjects

Variable	Characteristic	University of Washington (N=X)		Fenway Health (N=X)		All Subjects (N=X)	
		n	%	n	%	n	%
Ethnicity	Not Hispanic or Latino	x	x	x	x	x	x
	Hispanic or Latino	x	x	x	x	x	x
	Not Reported	x	x	x	x	x	x
	Unknown	x	x	x	x	x	x
Race	American Indian or Alaska Native	x	x	x	x	x	x
	Asian	x	x	x	x	x	x
	Native Hawaiian or Other Pacific Islander	x	x	x	x	x	x
	Black or African American	x	x	x	x	x	x
	White	x	x	x	x	x	x
	Multi-Racial	x	x	x	x	x	x
	Unknown	x	x	x	x	x	x
Rectal CT Symptomatic Status	Symptomatic	x	x	x	x	x	x
	Asymptomatic	x	x	x	x	x	x
Inguinal Lymphadenopathy	Yes	x	x	x	x	x	x
	No	x	x	x	x	x	x

Note: N=Number of subjects enrolled at the specified site.

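### With no antacid effect, the exploratory ITT antacid table (SAP Table 32) is expected to favour antacid users, because missing follow-up makes a man both a non-user and a failure

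*SAP*

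**What the plan says.** SAP 3.3.9 sets the timing: "Antacid use will be assessed at baseline, Visit 2, and Visit 3". One report is enough to be a user: "Subjects who report use of antacids at baseline or follow-up visits as documented on the Visit Documentation form will be classified as using antacids". Everyone else falls in the remaining class: "Subjects who do not report antacid use at all study visits will be classified as not using antacids". Nothing is said about a man whose follow-up antacid reports are missing.

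The antacid table shells in SAP Appendix 1 have two strata only; the implementation note says "the subgroup labels will be “No Antacid Use” and “Antacid Use". (That note cites Tables 32 to 34, whereas the antacid tables are 31 to 33, but the labels show which tables are meant.)

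SAP 6.5 deals with missing cure status, not with missing antacid status. For CC and PP: "Subjects with unknown microbiologic cure status will be excluded from the CC and PP population". For ITT: "For ITT analyses, such subjects will be included with their cure status imputed as microbiological failures". Under SAP 6.3.2.1, "The Intent-to-Treat (ITT) population includes all randomized subjects". The two rules meet in Table 32, "Microbiologic Cure at Visit 3 (Day 29) by Treatment Group and Use of Antacids - ITT Population".

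**The concern.** A man lost after Visit 1 has had one of three chances to report antacid use. Unless he reported it at baseline, 3.3.9 classes him as a non-user and 6.5 makes him a failure. A man whose use is first reported at follow-up has, by definition, been reached at follow-up. Imputed failures therefore collect in the non-user stratum for a reason unrelated to antacids.

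The exploratory objective (SAP 3.1.3) is to assess the effect of antacid use, among other factors, on Day 29 cure. In Table 32 that comparison is read across the All Subjects rows of the two strata. The artefact there favours users, so within that table it could mask a true reduction in cure.

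**Working it through.** **Plan figures used.** SAP 5 plans 274 enrolments, with at least 90% eligible for the primary analysis: 274 × 0.90 = 246.6, matching the stated 246. Its planning cure rates are about 95% (doxycycline) and 85% (azithromycin), which average 90% at 1:1 allocation. The plan gives no figure for antacid use or for this gap, so there is none to reproduce.

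**Assumptions, not in the documents.**
- L: share without a Day 29 result.
- p: share of fully followed men who report antacids at some visit.
- b: share who report them at baseline.
- f: share of the men without a Day 29 result who still had every chance to report.
- Cure c = 90% in users and non-users alike, with loss unrelated to antacid use.

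**Formulas.** Share of missing men classed as users: q = f·p + (1 − f)·b.

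Users = p·274(1 − L) + q·274L. Non-users = (1 − p)·274(1 − L) + (1 − q)·274L.

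ITT cure in a stratum = c × (followed men in the stratum) / (all men in the stratum).

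**Central case:** L = 10%, p = 15%, b = 7.5%, f = 0. Followed 246.6, missing 27.4.
- Users: 36.99 + 2.06 = 39.0; cure 0.90 × 36.99/39.0 = 85.3%.
- Non-users: 209.61 + 25.35 = 235.0; cure 0.90 × 209.61/235.0 = 80.3%.
- Gap: +5.0 points, with a true effect of zero.

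**Range at p = 15%.**

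| Change from the central case | Gap (points) |
|---|---|
| L = 5% | +2.6 |
| L = 15% | +7.2 |
| 20% of use reported at baseline (b = 3%) | +8.2 |
| 80% of use reported at baseline (b = 12%) | +1.9 |
| All use reported at baseline (b = 15%) | 0 |
| Half of the missing men gave full reports (f = 0.5) | +2.4 |

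If true cure were 85% in users and 90% in non-users, the central case would show 0.85 × 36.99/39.0 = 80.5% against 80.3%, or +0.2 points instead of −5.

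**Second parameterisation.** Suppose 5% report at baseline, a further 5% of followed men first report at follow-up, and 10% are lost. The gap is then +4.6 points, or +3.4 if half of the missing men gave a Visit 2 report. Across a grid of baseline shares from 0 to 20% and new-report shares from 0 to 20%, at 5% and 10% loss, the gap ran from 0 to 11 points and was never negative.

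In simulated trials of 274 men at 10% loss, with both shares at 5 to 10%, users had the higher ITT cure in 69% to 85% of trials. With status taken from the baseline report alone, that was 52% to 53%. The CC version showed no gap (0.00 to 0.03 points).

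**Arm differences.** In the central case a true 10-point difference becomes 10 × 36.99/39.0 = 9.5 points in users and 10 × 209.61/235.0 = 8.9 in non-users.

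**The case against.** The case for leaving the table alone has several parts.

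- **The 10% is not a loss rate.** SAP 5 gives it as the share not eligible for the primary analysis. By SAP 6.3.2.2 that includes eligibility violations and negative baseline NAATs, and such men can have Day 29 results. This stands: 10% is an upper planning value for missing Day 29 data.
- **A missing swab result is not a missing antacid report.** Follow-up data, including medications, can be taken by phone while the swab is mailed (Protocol 7.3 and 7.4). Early termination visits repeat the Visit 3 assessments where possible (Protocol 7.5). This stands and shrinks the gap, to +2.4 if half of the missing men reported fully.
- **The comparison is not tested.** The shell prints arm differences within each stratum. SAP 6.4 says the study is not powered for definitive subgroup claims. With about 39 users the standard error of the gap is about 6.2 points, so +5 is within noise. This stands as to consequence, but the bias remains, and the user versus non-user comparison is what the objective asks for.
- **The wording of 3.3.9 is ambiguous.** It could require a negative report at every visit. A lost man would then have no category, so a rule is still needed.

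A reader might infer more than this. One inference is that Table 32 will certainly show users doing better; the result holds in expectation only. Another is that a real antacid effect would be lost to the trial; Tables 31 and 33 do not carry the artefact. A third is that the table would suggest antacids modify the treatment difference; 9.5 against 8.9 points is too small to matter.

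**Conclusion.** The point holds, and it is minor. Read together, SAP 3.3.9 and 6.5 give Table 32 an expected gap in favour of antacid users when there is no antacid effect. The direction follows from the rules, provided some men lack both a Day 29 result and a complete set of antacid reports, some use is first reported at follow-up, and loss is unrelated to antacid use. The size cannot be fixed from the documents: +5 points is the figure for a full 10% lost after Visit 1, and roughly half that is as plausible.

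Nothing here supports a concern about the primary result. That rests on the CC population, which excludes unknown cure status and does not use antacid status.

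**What to change.** Drop Table 32 and report the antacid subgroups in CC and PP only (Tables 31 and 33). This removes the artefact at the cost of one exploratory table.

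If an ITT version is wanted, there are two alternatives, each a small edit to SAP 3.3.9 and the shell with no new data:

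- **Add an Unknown row** for every man without a follow-up antacid report, whatever he reported at baseline. Moving only the lost men with no reported use does not work. Lost baseline reporters would remain as users counted as failures (85.3% in the central case) while non-users would hold no lost men (90.0%), a reverse gap of about −4.7 points. The cost is that the two strata no longer sum to all randomised men. A small gap can also remain from men who reported at Visit 2 but not at Visit 3, since they had fewer chances to report.
- **Define the ITT strata by the baseline report alone.** The expected gap is then zero. The cost is that use first reported at follow-up is ignored.
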